4.2 PARTICIPANT SELECTION

4.2.1 INCLUSION CRITERIA

Patients interested in study participation must meet all of the following inclusion criteria:

- May be male or female
- Must be between 18 years and 65 years of age
- In the opinion of the investigator, must be medically able to undergo the administration of study material determined by laboratory tests obtained within 2 weeks before baseline for which the investigator identified no clinically significant abnormality.
- Be able to comprehend the informed consent document and provide consent for participation
- Females of childbearing potential must:
 - have a negative pregnancy test at screening
 - agree to not become pregnant or breastfeed for the period of the study through 1 month after completion of the study
 - be willing to use a reliable form of contraception during the study
- Have healthy skin as determined by the PI.
- Be willing and able to comply with the scheduled visits, biopsy/injection procedures, wound care instructions treatment plan, and other study procedures for the duration of the study.

4.2.2 EXCLUSION CRITERIA

Patients meeting any of the following criteria will be ineligible for study participation:

- Having received any investigational drug within 30 days prior to study entry
- An allergy history to any study materials including local anesthetic, antibiotics, antimycotics, dimethyl sulfoxide, human albumin, or bovine constituents, or hetastarch
 - Specifically: subjects allergic to penicillin, streptomycin, amphotericin will be excluded in addition to those listed above.
- Pregnant, lactating, or trying to become pregnant
- A history of keloid formation
- An active nonhealing wound

- Having a significant medical history that the investigator feels is not safe for study participation (for example, some forms of autoimmune conditions, metastatic cancer, infectious diseases such as HIV, HTLV I/II, Hepatitis B, Hepatitis C). Biopsies taken from individuals with infections that are not allowed to enter the cell therapy core will make it such that these individuals cannot participate.
 - Specifically we will exclude those with autoimmune diseases affecting the skin such as lupus.
- Having current skin diseases (i.e. extreme and active eczema, psoriasis, lichen planus) that the investigator feels is not safe for study participation
- A diagnosis of uncontrolled diabetes
- Active smoker during the study
- We will also exclude those who are on chronic immunosuppressive therapies such as oral steroids, but also those on chronic topical steroids in the area of investigation.

4.2.3 PARTICIPANT RECRUITMENT

Participants may be recruited if they are under the direct care of the PI or are referred by other providers who have identified the potential participant, asked their permission to be contacted, and then passed their information to the investigator. Additionally, participants may be recruited from those patients who were previously enrolled in a dermatologic study within the department and who gave their permission to be contacted regarding participation in future studies.

Participants will be approached by their physician after routine clinical encounters, in the privacy of the exam room, regarding their interest in participation in the study. In addition, potential participants may respond to IRB-approved recruitment flyers located throughout Johns Hopkins Department of Dermatology and Johns Hopkins Hospital.

4.3 INFORMED CONSENT

Interested potential participants will be given an appointment in the Cutaneous Translational Research Unit located at the Johns Hopkins Outpatient Center. At the appointment, they will be given the consent form and as much time as needed for them to review and ask questions about the study. To assess for understanding, the investigator will ask the participant to briefly summarize the study. The consent form may be provided for them before the appointment to allow them ample time to review the document. Non-English speakers will not be enrolled at this time. No screening or study related activities will take place until informed consent has been obtained.

4.4 PARTICIPANT REMOVAL CRITERIA

Participants will be removed from study if they request to be removed from study after signing consent but prior to administration of their autologous fibroblasts. The investigator may remove a participant from study due to lack of compliance to study directions, inappropriate behavior in clinic such as hostility to staff or the novel acquisition of an exclusionary criteria, for example. Such subjects will be replaced for the goal of attaining an adequate sample size for the study.

4.4.1 PARTICIPANTS WHOSE STUDY PARTICIPATION ENDS PREMATURELY

If a participant withdraws from the study prior to excision of the fibroblast injection sites, we will make a concerted effort to contact that patient. We will stress to the participant that this is an experimental therapy and that excision is the safest endpoint. We have also included this in the informed consent.

Study participation might also end prematurely if laboratory expansion of fibroblasts is not successful. There are many potential reasons for a failure to generate aliquots of fibroblasts of the desired cellular number from both volar and non-volar fibroblasts. These might include for example failure to simply have fibroblasts expand, an accidental infection during cell culture, a failure of release testing or the chance that fibroblasts are expanding so slowly the full cadre are not available before 40 days of expansion. If for any of these reasons either or both fibroblasts populations (volar and non-volar) are not available, then the subject will be discharged early from the study. No repeat biopsies will be done to avoid any potential injury to the patient in the context of a potential human error in sample processing. Subjects will be paid for all of the visits they kept.

4.4.2 TREATMENT FAILURE

For purposes of this study, treatment failure will be defined as no increase in epidermal thickness or induction of volar specific genes such as KRT9.

4.5 STUDY DURATION AND REQUIRED VISITS

Participants will be considered ‘on-study’ once informed consent has been obtained. The duration of the study for each participant will begin at the time of consent and continue until completion of the final study evaluation.

For Phase One participants: At a minimum, there will be 7 study visits, including screening procedures. At a maximum, there will be 12 study visits over a period of 10 months.

For Phase Two participants: At a minimum, there will be 4 study visits, including screening procedures. At a maximum, there will be 14 study visits over a period of 12 months.

4.6 PAYMENT AND REMUNERATION

Phase One: Participants will receive \$150.00 per completed milestone (maximum payment of \$600). The four milestones are: a) Screening and baseline biopsy; b) Graft injection; c) Graft monitoring and removal; and d) Final evaluation.

Phase Two: Participants will receive \$150.00 per completed visit milestone (maximum payment of \$600). The four milestones are: a) Screening and baseline biopsy; b) Graft injection; c) Graft monitoring and removal; and d) Final evaluation.

These sums will be provided in cash or gift card form.

Participants will not be paid for missed milestones unless visits are rescheduled within 7 days. Also, participants may forfeit their bonus if they miss more than 2 visits that are not rescheduled within 7 days. Participants may forfeit their bonus for final evaluation if they do not complete the study.

4.7 COSTS

Participants will not be responsible for any study related costs. [name] AFIRM2 grant and NIH NIAMS R01 will cover all study costs.

5. STUDY SCHEDULE

5.1 SCHEDULE OF EVALUATIONS

See Appendix I for a table containing the full schedule of study evaluations.

5.2 STUDY VISITS

5.2.1 SCREENING AND INFORMED CONSENT VISIT (TO BE OBTAINED WITHIN 14 DAYS OF BASELINE/BIOPSY VISIT)

During the first scheduled appointment, the research protocol will be discussed with the potential participant. We will review exclusion and inclusion criteria and provide the participant with an informed consent document. After reviewing it together, assessing the patients understanding of the material and answering any questions that they may have, informed consent will be obtained from the subject.

Once informed consent has been obtained, the following evaluations will be done:

- Medication review
- History and limited physical examination
- Vital signs including BP, pulse, and respirations

Screening blood tests obtained at this visit will include:

- Serum HCG for females of child bearing capacity

- Hopkins test code 4133 Donor Serology Panel which requires 2 serum tubes and 1 EDTA tube for the following studies:
 - HIV Screen
 - HIV1 and HIV2 Antibody
 - HIV nucleic acid
 - For the HIV test only, the participant will be given the State of Maryland HIV consent form as part of that process. (If this test is positive, it does not always mean that the participant is infected with the HIV virus. It means the participant will need further testing and the participant will receive counseling).
 - HTLV I/II
 - Antibody test
 - Hepatitis B
 - Hep B Surface Ag
 - Hep B Core Antibody
 - Hepatitis C
 - HEP C Nucleic acid
- For HIV and Hepatitis B and C tests, the law requires us to report positive tests to the health department. Result of the blood sample tests must be negative for the participant to participate in this study.

The participant's next study visit will be scheduled by the study team as soon as all of the screening laboratory test results are received. The participant will be notified by telephone of the appointment.

5.2.2 BASELINE/BIOPSY VISIT (VISIT #1) (STUDY DAY 0)

At this study visit, the following will be obtained:

- History and limited physical examination
- Review of eligibility/screening test results
- AE Assessment

The investigator will identify 1 area on the participant's sole and 1 area with suitable non-volar skin, like the scalp, to biopsy and clinical photographs will be taken of the sites. (See Appendix II). Local anesthesia consisting of lidocaine with epinephrine will be used and the investigator will perform 3 skin biopsies (1 punch of volar sole skin and 2 punches of non-volar skin). These will be a standard 4mm punch style biopsy (or smaller) taken from the participant's skin to a depth of 2mm.

One suture will be placed in each biopsy site to aid healing. The biopsy sites may be from the participant's sole and dorsum of foot (or any site with suitable volar/nonvolar skin). The participant may provide their preference of biopsy sites.

The amount of time taken for the biopsies is about 20 minutes. After the biopsy is completed, it is sent to the Hopkins Cellular Therapy Core (see IND CMC section) where the fibroblasts cells will be grown. (See Appendix III for specimen preparation and handling.)

Before leaving, participants will receive a biopsy site care information sheet (See Appendix IV) with contact information in the event of any adverse event. They will also be given a return appointment for suture removal at this time.

During the baseline visit, the 3 graft injection sites will be identified. To optimize future localization, very small tattoos, the size of a pinpoint or freckle, will be made using tattoo ink. Please see tattoo procedure in section 5.2.4.

5.2.3 SUTURE REMOVAL VISIT (VISIT #2) (STUDY DAY 14 +/- 2 DAYS)

The participant will return to clinic for suture removal. At this study visit, the following will be obtained/performed:

- Vital signs including BP, pulse, and respirations
- Biopsy site/AE assessment
- Biopsy site suture removal

The participant will be given their graft administration visit appointment at this time.

5.2.4 GRAFT INJECTION VISIT PHASE ONE VISIT #3 (STUDY DAY 30 +/- 7 DAYS) OR PHASE TWO VISITS #3-6 (STUDY DAYS 30, 37, 42, 59)

The participant will return to the clinic on or near Day 30 for their graft injection.

Participants will have the following assessments done:

- History and limited physical examination
- Females of child bearing potential will have a urine pregnancy test done prior to administration of the investigational cells to ensure that they are not pregnant.
- Clinical photographs will be taken of each of these 3 sites before the investigational product is administered. These photographs will be used throughout the study to document changes in the skin as well as aid in location of the site at subsequent visits. Photograph files will be coded with the participant's unique identifier. The participant will not be identifiable from the clinical photographs.

Together with the study investigator, a site for injection of the subject's grown fibroblasts will be chosen. The injections will be placed by the investigator into the three sites mutually identified (e.g. the three injections will be placed on one of

the participant's buttocks, or non-buttocks area as above). The injection sites will be spaced at least 5 cm from the center of any neighbor and may be divided between left and right buttocks or non-buttocks area as above to ensure a lack of overlap.

Identification of injection sites to optimize future localization will occur through these steps:

- We will identify distances and angle from anatomical landmarks such as the sacroiliac joint.
- We will draw anatomical landmark maps with transparency paper used for projections. We will circle landmarks so that the transparency can be directly placed on the subjects buttocks or non-buttocks area as above in a repeatable orientation, and also identify injection sites.

To further enhance our ability to localize injection sites, we will use a small volume of ($x < 0.025$ ml) tattoo ink to mark areas of cellular injection:

Small tattoos on the skin are routinely performed by radiation oncology to orient radiation fields. These tattoos are permanent for patients, but are subtle and difficult to notice without a trained eye. (See Figure 1)

[figure not shown]

Figure 1: Tattoo mark on figure at end of arrowhead appears vaguely bluish in the subepidermal compartment.

[name], the PI, received instruction from [name], MD-PhD and [name], Assistant Chief Therapist for Radiation Oncology at the Johns Hopkins Hospital. We will only tattoo areas which will be removed in the final excision of the area injected with cells. Therefore the subject will be left with no mark and only temporarily have the tattoo. Also, we will strictly follow the clinical protocol which has proven extremely safe and easy, without complications in its routine clinical use.

1. We will use the exact same pigment used by Radiation oncology which is sold for human use (Black Tattoo ink, Reorder #VIP-1PI, by VanArsdale Innovative Products, Inc.)

2. A single drop will be dropped into a sterile 25gX5/8" needle at the open hub which normally connects with the syringe. A portion of the drop volume is pulled by capillary action to the needle tip.

3. The needle is then inserted gently into human skin with the bevel up at a 30 degree angle to the skin, and only to a depth where the full bevel is covered. The pigment leaches out again only by capillary action and is not pushed out. The needle is immediately removed after insertion. The estimated amount of pigment solution deposited must be much lower than a droplet size of 0.025ml(1).

4. No local care is necessary. The tattoo will be performed at the time of initial biopsy for skin harvesting to allow time for it to fully integrate without inflammation in to the skin before cellular injection. In the rare and unusual case where cells fail to grow or are rejected for any reason and are not available for injection, then the subject will be given the option of a small punch biopsy in those 3 areas of cellular injection to remove the miniscule dot of pigment (See Figure 1). In this way all subjects will be guaranteed the option of full removal of pigment, though normally radiation oncology patients retain the tattoos indefinitely.


If a subject refuses consent for the tattoo marker, but is otherwise willing to complete all other study procedures, then we can use the palpated sacral hiatus, and initiation of the gluteal cleft as 2nd and 3rd universal landmarks. In addition, we will maximize the use of individual landmarks such as nevi, seborrheic keratoses, scars and hemangiomas which are found on human skin. In previous studies that the PI has performed(1), he has used exactly this method for the injection of hyaluronic acid to identify sites months later and had universal success at identifying injection sites. Also, to enhance our ability to identify sites we will not limit injections to one side of the buttocks (or non-buttocks area as above) to enhance the available number of landmarks and ensure proper identification in subsequent visits after the injection. Finally, we will frequently also consult clinical photographs (photographed with rulers) of the injection site taken on the day of injection to optimize our ability to correctly map injection sites.

We will avoid injection into the skin above the ischial tuberosity to minimize discomfort and risks of ulcers

Phase One: Single Dose Injection

After numbing the participant with anesthesia described in Visit 2, two of the sites will be injected with 0.7-0.8 mls of media (5% DMSO, 6% hetastarch and 2.5% human serum albumin) containing 30-40 million autologous fibroblasts into a small area about 3-4mm injection area subepidermally at the level of the epidermis-

dermis junction. The third site will be injected with the same volume of media containing no autologous cells.

Phase Two: Intermittent Dosing Regimen

We do not propose to increase the total number of cells injected, but to inject fewer cells more often. At the PI's discretion, the subject may receive injections of the dosing regimen or injections of 10% DMSO.

Two of the three treated sites will receive cells. A total of 4 injections may maximally occur; the first will always include cells for these sites. The remaining 3 injections may include vehicle and up to 10% DMSO instead of cells administered within 30 days after injection of cellular product.

The third control site will not receive cells but instead be injected with the same volume of media or up to 10% DMSO, containing no autologous cells; it, may receive intermittent administration of vehicle media or up to 10% DMSO with the same schedule as above for the two sites receiving cells. The 10% DMSO media will be RIMSO-50, a FDA-approved product for the use in interstitial cystitis and delivered intravesically. The injections may be spaced in any manner over the 30 days. The dose volume will be determined on the basis of results from Phase One. A range of dose volumes may be tested but the total number of injected autologous fibroblasts will not exceed 30-40 million. As in Phase One, the dose will be prepared by appropriately trained and qualified personnel in the cellular therapy core and administered by the PI. We will be using an FDA approved product (RIMSO-50), because we unexpectedly found in our animal studies that the DMSO in our vehicle actually enhances cellular engraftment. We propose to inject no more than 10% DMSO at a volume of less than 1 ml into the skin not more than 3 times. We will only inject the areas where the vehicle or cells were previously injected (3 approximately 6 mm circles). We confirm that this study will not proceed until this Protocol Amendment is granted approval from the Johns Hopkins Medicine Institutional Review Boards.

The following information will be recorded by the investigator administering the cells (see Cell Administration sheet in Appendix V):

- Vial identification numbers
- Date of administration
- Times of administration
- Total cell dose
- Injection sites

Superficial skin scrapings are routinely done in dermatology and may be employed before or after we inject cells in order to potentially enhance tissue repair and regeneration. They might also occur during graft evaluations in subsequent visits. Scrapes will be done at injection sites using two gentle steady strokes of a sterile disposable #15 blade or curette. This wounding technique was specifically chosen to eliminate bleeding and infection risks.

Participants will be observed for 60 minutes following the cell administration for adverse events. At two points in this interval we will perform blood pressure and pulse measurements to monitor for an allergic reaction

Upon release of the subject, we will include instructions to keep the injection site covered with a padded dressing for 24-48 hours after injection. Especially during that time and afterwards, the subjects will be instructed to avoid manipulating the site for example by scratching, ice or topical remedies. If the subject has discomfort for which they desire therapy, we will ask them to return to the clinic for evaluation by a study team member at which time we will assess for adverse events.

Participants will be instructed to maintain diaries of injection site symptoms and events which they will bring to each subsequent appointment until the graft has been excised. (See Appendix VI for injection site diary.)

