At each of the monitoring visits, the study team will obtain:

- Vital signs including HR, RR and BP
- Clinical photographs of the injection sites
- Measurements of injection site thickness and areas of increased thickness via Optical Coherence Tomography (OCT) or SkinFibroMeter. OCT is a non-invasive means of capturing images of superficial layers of the human skin (see Figure 8). From these images, thickness of the epidermal layer will be calculated. 3 independent measurements from each injection site in each subject will be made at every visit so that statistics can be performed (see below). SkinFibroMeter is a non-invasive, portable device utilizes an indenter that is briefly pressed on the skin. The resistance of short-term load from the skin tissue will be read by the device and the induration value of Newton will be calculated. Some visits might not include OCT imaging or SkinFibroMeter given operator and machine availability. Some exceptions can be made for unusual life events for missing a study monitoring visit.
- AE assessment/ symptom diary review

Monitoring will continue on a monthly basis for up to 5 visits in order to assess the participant’s progress and for any adverse events. At each monitoring visit, a repeat gentle skin scraping may be performed.

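### Phase Two has no stated allocation rule and section 9.2 no analysis that could show whether serial dosing beats single dosing or whether curettage helps (objective 5, efficacy part of objective 4)

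*Combined protocol and SAP*

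**What the plan says.** **The questions.** Section 2 lists the efficacy of serial dosing (with its safety) as secondary objective 4 and the efficacy of curette wounding as objective 5. The abstract wants Phase Two to find the best delivery method and to test whether wounding improves engraftment. Section 3 sets multiple against single injection. Section 4.1 adds 80 participants to the first 20 so that the Phase Two objectives can be met.

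**The regimen.** Phase One is fixed: "Phase One: Single Dose Injection". For Phase Two, section 5.2.4 says that at the PI's "discretion, the subject may receive injections of the dosing regimen or injections of 10% DMSO". At the two cell sites there may be up to four injections; "the first will always include cells for these sites", but "The remaining 3 injections may include vehicle and up to 10% DMSO instead of cells". Spacing within the 30 days is left open, and "The dose volume will be determined on the basis of results from Phase One".

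**Curettage.** Section 3 gives it to some of the participants, without a number or a selection rule. Section 5.2.4 says: "Superficial skin scrapings are routinely done in dermatology and may be employed before or after we inject cells". Section 5.2.5 adds: "At each monitoring visit, a repeat gentle skin scraping may be performed".

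**The analysis.** Section 4.1.1 has randomisation in its title but describes only blinding. Section 9.2 contains a within-participant t-test for early graft removal, an end-of-study volar versus non-volar t-test for thickness and for KRT9 mRNA, and average areas of thickening. Its one power statement arrives at 3 participants.

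**The concern.** A claim that one way of delivering the cells works better than another needs groups that differ only in delivery, and an analysis that compares them. The plan provides neither.

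The volar versus non-volar contrast is made within a participant, whose two cell sites are described as following the same option. It isolates cell type and is silent on what the regimen or the scraping contributed.

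Groups formed by choice may differ at the outset, and here the choice can also follow results. Clinicians are unblinded (section 4.1.1), data are re-analysed as each participant finishes (section 9.2), and scraping is optional at the visits where thickness is measured (section 5.2.5). Blinded measurement does not remove that kind of bias.

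At stake is whether healthy volunteers, who are told to expect no personal benefit (section 6.3.1), undergo injections and excisions for two efficacy questions that the data could not settle.

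**Working it through.** **1. The plan's own sample size.** Inputs from section 9.2: difference 2, SD 0.5, alpha 0.06, power 0.8; sidedness is not stated. The standardised difference is 2/0.5 = 4. For a two-sample t-test with n per group, the noncentrality is 4 × √(n/2) on 2n − 2 degrees of freedom. At two-sided alpha 0.06, power is 0.630 for n = 2 and 0.963 for n = 3. The stated 3 is therefore the smallest n that reaches 0.8. It belongs to a 4-SD contrast, and nothing ties it to a regimen or curettage effect.

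**2. Questions against planned analyses.**

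| Question | How groups arise | Analysis in 9.2 |
|---|---|---|
| Volar versus non-volar | Two sites in each participant | t-test, thickness and KRT9 |
| Serial versus single dosing | PI's choice within Phase Two, or Phase One versus Phase Two | None |
| Curettage versus none | Optional; no selection rule | None |

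Because only the first injection must contain cells, the PI's choice appears also to decide who receives cells repeatedly and who receives them once. That is an inference from reading the sentences together.

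**3. Phase One as comparator.** The two cohorts are enrolled one after the other, without randomisation, and 9.2 plans no test between them. Phase Two may also change dose volume and DMSO content, and not all of its 80 participants need receive cells serially. A 20 versus 80 comparison would therefore not be single versus serial dosing, and no detectable difference is given for it. It says nothing about curettage.

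**4. What 80 participants could detect if randomised.** Assumptions: outcome is the within-participant volar minus non-volar difference, in units of its own SD; two-sided alpha 0.05; power 0.80; the splits are mine. Detectable difference = δ × √(1/n₁ + 1/n₂), where δ is the noncentrality that gives 80% power.

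- 40:40: 2.837 × 0.2236 = 0.63 SD
- 20:60: 2.837 × 0.2582 = 0.73 SD
- 10:70: 2.837 × 0.3381 = 0.96 SD
- Three groups, 80/3 ≈ 27 each, per pair, unadjusted: 2.855 × 0.2722 = 0.78 SD
- The same with Bonferroni, alpha 0.05/3 = 0.0167: 3.328 × 0.2722 = 0.91 SD

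Failed cell expansion leads to discharge (section 4.4.1). With 60 evaluable at 30:30 the figure is 0.74 SD; with 40 at 20:20 it is 0.91 SD. All of these describe the power of the remedy. They do not measure bias in the current plan.

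**5. What selection could do.** The documents give no figure for prognostic imbalance between discretionary groups. Purely as an assumed range, imbalances of 0.1, 0.2, 0.3 and 0.5 SD at 40:40, with no true effect, would make a nominal two-sided 5% test reject in about 7%, 14%, 26% and 60% of trials.

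**The case against.** The best defence is that this is a single-arm Phase I feasibility study with tolerability as primary outcome (sections 4.1, 9.1, 9.2.1), and that section 6.3.2 leaves optimisation of dose and frequency to a later, more formal trial. Objective 4 as worded does not demand superiority over single dosing, and the volar versus non-volar test in serially dosed participants partly meets it. This stands, and it makes a descriptive reading reasonable. But the protocol does not adopt that reading: it keeps the word efficacy, frames Phase Two comparatively in the abstract and section 3, and enrols 80 people for it.

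The schemas cited in sections 5.2.5 and 8.1 are not in the text available and may show groups. That limits the statement about allocation. It would not supply the comparison missing from 9.2 or remove the discretion wording.

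Some stronger readings are not supported:

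- A reader might infer that curettage is expressly at the PI's discretion. That word applies only to the regimen-or-DMSO choice; for scraping the text is permissive, with no selection rule.
- A reader might infer that Phase Two yields no efficacy information, or has too few participants. The volar contrast remains, and step 4 shows that numbers are not the obstacle.
- A reader might see a contradiction in the control site being optionally re-injected yet "with the same schedule as above for the two sites receiving cells". It reads consistently: if repeated, then on that schedule. Likewise, cell-free later injections are a permitted alternative, listed in section 3 as well.
- In the plan's favour, a reader might take the KRT9 contrast to be secured by blinding. Section 4.1.1 promises numbered labels only, but Appendix VII puts the cell identity on the excised-tissue tubes, so that reassurance cannot be given.

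**Conclusion.** The point holds for the comparative questions behind objective 5 and the efficacy part of objective 4. Followed as written, the plan can show a volar effect under the regimens used. It cannot show that serial dosing beats single dosing or that wounding adds anything, and a Phase One versus Phase Two contrast would be unplanned, sequential and confounded.

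The reach is those two questions among up to 80 of the 100 planned participants; their safety data and volar contrast remain usable. The size of any selection bias is unknown. The conclusion assumes that the schemas contain no allocation rule. This should be corrected, but it does not threaten the primary outcome. Confidence is medium because of the unseen schemas.

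**What to change.** **Preferred.**

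1. Once the investigators have fixed which already-permitted Phase Two options are to be compared, assign participants to them, and to curettage yes or no, by a randomisation list.
2. Record the assigned option, DMSO content and scraping on the Appendix V sheet, which now has no field for DMSO content or scraping, or elsewhere on the CRF.
3. Add to section 9.2 a between-group comparison of the within-participant volar minus non-volar difference, for regimen and for curettage, with a multiplicity rule if more than two options are compared.

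**If discretion is kept.** State in section 2 and section 9.2 that the efficacy parts of objectives 4 and 5 are descriptive, and that no conclusion on serial versus single dosing or on wounding will be drawn.

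**In either case, reconcile:**

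- the labelling in section 4.1.1 with that in Appendix VII;
- whether scraping belongs to Phase Two only (abstract, section 3) or to both phases (sections 5.2.4 and 5.2.5, which do not limit it).

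**Cost.** The preferred route needs an amendment, a list, a few CRF fields and SAP text, with no participants beyond the planned 80 and no procedure that is not already permitted. Its drawback is that the PI gives up case-by-case choice. The fallback costs only wording. No dose, schedule or clinical rule is proposed.
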